4.10 DATA ANALYSIS

A descriptive analysis will be performed on the changes in vital signs observed during the operation (if any). A direct comparison and calculation of the averages will be made between the values observed in both the postoperative analgesia evaluation and the transoperative bleeding assessment.

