The removal of third molars is one of the most frequently performed procedures in dentistry, and can be carried out in a hospital setting under general anesthesia. In such cases, local anesthetics are often administered at the surgical site in addition to general anesthesia, to promote better hemostasis and postoperative analgesia. Bupivacaine is a local anesthetic commonly used in these situations. However, its known cardiotoxic and neurotoxic effects, as reported in the literature, have led to increased interest in safer alternatives, such as ropivacaine. **Objective:** to evaluate whether there is a significant difference between bupivacaine and ropivacaine in terms of postoperative analgesic efficacy, intraoperative hemostasis, and patient vital signs during the intraoperative period. **Materials and Methods:** This was a randomized, controlled, split-mouth clinical trial. The sample size was based on a similar previously published study and included 15 participants ($n = 30$). As this study also follows a split-mouth design, each of the 15 patients underwent two tooth extractions. All patients had indications for the removal of both lower third molars under general anesthesia. Surgical extractions were performed in a single session, with bupivacaine (Group A) administered at one surgical site and ropivacaine (Group B) at the other. The procedures were carried out at the Hospital de Clínicas de Porto Alegre. Vital signs were continuously monitored by the same anesthesiology team, with data collected at the time of drug injection (before and immediately after), as well as one minute and five minutes post-injection. Intraoperative bleeding was measured by calculating the volume of blood aspirated into the collection vial, from the time of incision to the final suture, at each surgical site. To minimize systemic interference from the anesthetic agents, their administration was alternated between patients. Postoperative analgesia was self-reported by the patients using a Visual Analog Scale (VAS) for each side at various postoperative time points. A descriptive analysis will be conducted on the clinical data obtained through these measurements.

Key-words: Third Molar; Anesthetics, Local; Surgery, Oral

SUMÁRIO

SUMMARY	5
1 INTRODUCTION	6
2 LITERATURE REVIEW	8
3 OBJECTIVES	10
4 METHODOLOGY	11
4.1 ETHINCAL ASPECTS	11
4.2 TYPE OF STUDY	11
4.3 LOCATION	12
4.4 SAMPLE	12
4.5 PREOPERATIVE CONDUCTS	13
4.6 SURGICAL TECHNIQUE	13

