As a result, there has been a search for a new anesthetic substance that combines the advantages of bupivacaine (high potency and long duration) while minimizing its disadvantages (lower cardiac toxicity and arrhythmogenic properties). Among the substances found, levobupivacaine and ropivacaine stand out.¹⁶

Levobupivacaine hydrochloride shares properties with racemic bupivacaine, but

with lower cardiac toxicity. Its use is more common in the medical field, often combined with epinephrine. However, its use is not widespread in dentistry.¹⁷

Ropivacaine hydrochloride also has properties similar to racemic bupivacaine, but with reduced cardiac toxicity. Furthermore, it has intrinsic vasoconstrictor properties, minimizing the need for additional vasoconstrictors during its administration.^{16,18}

Among the main benefits of using local anesthetics are comfort, analgesia, vasoconstriction (when combined with vasoconstrictors) and reduce postoperative pain, what makes its use is recommended even during procedures under general anesthesia.¹⁹ Even with the proven greater safety of anesthetic agents such as levobupivacaine and ropivacaine, bupivacaine still dominates hospital dental practice, despite so much evidence against its use.²⁰ Moreover, there is no protocol or commercial formulation for its use in anesthetic tubes, further hindering the use of these alternative anesthetic agents in dentistry. Therefore, this study aims to evaluate whether there is a significant difference between bupivacaine and ropivacaine in terms of postoperative analgesia, intraoperative hemostasis, and the patient's vital signs during the procedure.¹⁶

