3 OBJECTIVES

3.1 GENERAL OBJECTIVE

This study aims to evaluate whether there is a significant difference between 0.5% bupivacaine with 0.2MI of epinephrine and 0.75% ropivacaine with 0.2MI of epinephrine in terms of postoperative analgesic capacity, intraoperative hemostasis and the patient's vital signs during the transoperative period.

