3.2 SPECIFIC OBJECTIVES

- Measure the amount of intraoperative bleeding (in mL) during procedures performed with 0.5% bupivacaine with 0.2 mL of epinephrine and 0.75% ropivacaine with 0.2 mL of epinephrine.
- Assess potential changes in patients vital signs during and after the administration of local anesthetics.
- Compare the levels of postoperative discomfort associated with anesthetic agents using a visual analog scale (VAS).

JUSTIFICATION

Despite the well-known cardiotoxic and neurotoxic effects of bupivacaine, it continues to be widely used in oral and maxillofacial surgery. This study aims to compare and evaluate the feasibility of using a less toxic anesthetic agent in lower third molar removal surgeries under general anesthesia.

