4.1 ETHICAL ASPECTS

The study will be conducted in accordance with the Guidelines and Regulatory Standards of the National Health Council (Resolution No. 466/12), which establishes the ethical guidelines for research involving human subjects in Brazil.

The benefit of participating in the research is indirect, as the patient contributes to the discovery of scientific evidence that will serve as the foundation for safer and more effective treatment.

Patient personal data, collected through direct contact with the participant during the study, will not be disclosed, and confidentiality will be ensured for all participants. This data will be stored in a Google Drive spreadsheet linked to the researchers institutional email address.

Surgical procedures and the participant's participation in the project may present certain surgical and confidentiality risks inherent to participation, which are outlined in the Informed Consent Form (APPENDIX A).

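### The objective asks whether there is a significant difference, but the stated analysis (description, and averages with no measure of uncertainty) cannot answer it

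*Protocol*

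**What the plan says.** The aim appears three times in inferential terms. The Summary sets out "to evaluate whether there is a significant difference between bupivacaine and ropivacaine in terms of postoperative analgesic efficacy", and continues with intraoperative hemostasis and vital signs. The Introduction (section 1) repeats it: "this study aims to evaluate whether there is a significant difference between bupivacaine and ropivacaine in terms of postoperative analgesia". Section 3.1 does so again: "This study aims to evaluate whether there is a significant difference between 0.5% bupivacaine", covering the same three domains.

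The analysis appears twice. The Summary closes with "A descriptive analysis will be conducted on the clinical data obtained through these measurements". Section 4.10 plans a descriptive analysis of changes in vital signs. For postoperative pain and intraoperative bleeding it says "A direct comparison and calculation of the averages will be made between the values observed". Sections 4.8 and 4.9 add only that the values will be recorded, compared and presented.

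Section 3.2 is more modest about vital signs: "Assess potential changes in patients vital signs during and after the administration of local anesthetics". Section 4.1 (sample calculation) gives 15 patients with two sites each. Section 4.9 has each side scored separately at five times, T0 to T4.

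**The concern.** The question and the stated analysis do not match. Whether a difference is significant can only be judged against the variation expected by chance, and neither the Summary nor 4.10 provides for that. A test or interval that is simply unnamed could be left to a statistical analysis plan. Here, however, the protocol states what the analysis will be, and that analysis stops short of its own objective.

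The trial would deliver six pairs of averages: bleeding, and VAS at five times. Two misreadings are open. Similar averages could be taken to show that ropivacaine does as well as bupivacaine, which is tempting because the justification in section 3 is to assess the feasibility of a less toxic agent. Or one time point with unequal averages could be taken as a drug effect. Nothing in the planned output would check either reading.

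**Working it through.** The protocol gives no effect size or standard deviation, so it has no figure of its own to reproduce here. The check asks how far averages from this design can move by chance.

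**Inputs**
- Pairs: n = 15 (section 4.1, sample calculation; split-mouth, one drug per side).
- Comparisons of averages: 1 for bleeding + 5 for VAS = 6 (sections 4.8 and 4.9).
- Unit: the SD of the within-patient differences, ropivacaine side minus bupivacaine side. The mean difference is taken as approximately normal.
- Assumed, not in the protocol: cutoffs of 0.25 and 0.5 SD, the correlation among VAS times, and a VAS difference SD of 1.5 to 3 points.

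**One pair of averages**
- Standard error = 1/√15 = 0.258 SD.
- No true difference, gap of 0.25 SD or more: 0.25/0.258 = 0.968; 2 × [1 − Φ(0.968)] = 0.333.
- No true difference, gap of 0.5 SD or more: 0.5/0.258 = 1.936; 2 × [1 − Φ(1.936)] = 0.053.
- True difference of 0.5 SD, observed gap below 0.25 SD: Φ(−0.968) − Φ(−2.905) = 0.165.

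So averages can suggest a difference that is not there, and can look alike when a difference exists.

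**Six pairs of averages, no true difference**
- If independent, the chance that at least one gap reaches 0.25 SD is 1 − (1 − 0.333)⁶ = 0.912.
- By simulation with bleeding independent and the five VAS times equally correlated at 0.9, it is 0.690. The range is therefore about 69% to 91%, depending on the assumed correlation.

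**What an interval would give**
- Paired t, 95% CI half-width: t(0.975, 14)/√15 = 2.145/3.873 = 0.554 SD.
- On the VAS, with the assumed SD: 0.554 × 1.5 = 0.83 and 0.554 × 3 = 1.66 points.

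**Cost of testing all six at 5% without adjustment**
- Independent case: 1 − 0.95⁶ = 0.265. Simulation with VAS correlation 0.9 gives 0.146.

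**The case against.** The best defence is that a direct comparison in 4.10 need not exclude a test. The word descriptive in that section applies only to vital signs. Each patient's two values are recorded, so an interval could be computed, and naming the method is often left to a statistical analysis plan. This is right as far as it goes: it would be wrong to say that 4.10 labels the pain and bleeding analyses descriptive, or that it forbids inference. But the Summary does apply that label to the measurements as a whole, and 4.10 attaches nothing but averages to the comparison. If inference was intended, the text still needs to say so.

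The cutoffs are also open to challenge. The protocol never says that a gap of 0.25 SD would be read as a drug effect, and it gives no SD. That stands: the percentages illustrate the problem and do not forecast how often this trial will err. The standard error and the half-width in SD units need no such cutoff.

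Finally, the contradiction could be removed by rewording the objective as descriptive. That is a coherent option. It would leave the question put in three places unanswered, though, when data that could address it are already being collected.

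**Conclusion.** The point holds and should be fixed before the data are analysed. The objective is inferential, the stated analysis is not, and with 15 pairs the gap matters: the standard error is 0.26 SD of the paired differences, and one pair of averages differs by 0.25 SD or more about one time in three by chance alone. This rests on n = 15, approximate normality of the mean difference and an illustrative cutoff.

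Two stronger readings should be avoided.
- A reader might infer that the specific objectives demand a formal comparison of every outcome. In section 3.2 the comparative wording covers VAS discomfort only. Bleeding is to be measured there, and its comparison comes from 4.8 and 4.10. For vital signs, description already fits 3.2, so only the wording of the general objective is out of line.
- A reader might infer that patients are promised a comparative result, because the ethics section speaks of "the discovery of scientific evidence that will serve as the foundation for safer and more effective treatment". That passage describes an indirect benefit of taking part. It neither shows what patients are told nor commits this trial to a comparative conclusion.

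**What to change.** **Section 4.10 and Summary.** Analyse the 15 within-patient differences (ropivacaine side minus bupivacaine side) in bleeding and in VAS at T0, T1, T2, T3 and T4. Use one paired method fixed in advance, for example the signed-rank test with its interval, or the paired t. Because the 0 to 10 VAS is always bounded, the choice should be made now and not left to depend on how the data look. Report each of the six estimates with its 95% CI. Either name one outcome and time as primary before analysis, or label all six exploratory; in the latter case, word the objective as estimation. State that a non-significant result does not show equivalence.

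**Summary, section 1 and section 3.1.** Say that vital signs will be described, to match 4.10.

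**Cost.** Some rewording and a paired analysis of data already planned; no extra patients, visits or measurements. The downside is that precision will look modest (half-width about 0.55 SD), and that six unadjusted 5% tests carry a family-wise error of about 26.5% if independent. That is the reason for naming one primary comparison or using the exploratory label.

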5 TIMELINE

The mandibular third molar removal surgeries under general anesthesia will be performed based on availability at the Oral and Maxillofacial Surgery Unit of the Hospital de Clínicas de Porto Alegre. Currently, two surgeries per week are available, and these will be conducted until the sample size is reached.

ACTIVITY/MONTH	01	02	03	04	05	06	07	08	09	10	11	12
BIBLIOGRAPHY REVIEW	x	x										
SURGICAL PROCEDURES			x	x	x	x						
DATA ANALYSIS							x	x				
COMPLEMENTAR Y LITERATURE REVIEW									x	x		
PRESENTATION OF THE FINAL PAPER										x	x	
WRITING AND SUBMISSION OF THE SCIENTIFIC ARTICLE												x

6 RESOURCES AND BUDGET

The transportation costs for research participants to attend their appointments will be covered by the researchers (including the cost of a municipal bus ticket for each appointment), as well as any other expenses incurred as a result of their participation in the study.

All costs related to the surgical procedure will be covered by the Hospital de Clínicas de Porto Alegre, through the Unified Health System (SUS). Postoperative medications will be reimbursed through the Unified Health System (SUS).

TYPE OF MATERIAL	MATERIAL	QUANTITY	PRICE	
			UNITARY	TOTAL
	Bus ticket	90	R\$ 4,80	432
	Total			R\$ 432,00

6.2 HUMAN RESOURCES

The bibliographic review and construction of the project will be carried out by the research team, as well as the surgical procedures and data analysis.

6.3 FINANCING SOURCES

The expenses necessary for the execution of the research project will be paid with the responsible researcher's own resources.

APPENDIX B – POSTOPERATIVE CARE PROTOCOL

- Bite firmly on a gauze pad for 20 minutes in case of delayed bleeding.
- Eat a soft, cold, or ice-cold liquid diet for 48 hours. Avoid grainy or bran-based foods until the suture is removed.
- Apply ice to the face over the surgical site for 20 minutes for the first 24 hours, followed by a 20-minute rest.
- Rest, keeping your head elevated above the rest of your body.
- Avoid strenuous physical activity and sun exposure for 7 days.
- Brush your teeth normally 24 hours after surgery.
- Gently brush the surgical site until the suture is removed.
- Do not rinse your mouth for 48 hours.
- Avoid spitting.
- Do not smoke until discharge from surgery.
- Medication:
 - Paracetamol 1g, 2 tablets every 6 hours for three days.
 - Ketorolac tromethamine 10mg, 1 tablet every 6 hours for three days.
 - Clindamycin 300mg, 2 tablets every 6 hours for seven days.
 - Rinse with 10mL of 0.12% chlorhexidine digluconate aqueous solution for 1 minute every 12 hours for seven days, starting 24 hours after surgery. – see medications.
 - In case of persistent bleeding, severe pain, or fever (temperature greater than or equal to 37.8°C), contact your doctor.

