4.6 SURGICAL TECHNIQUE

The procedure will be performed in a hospital setting, where patients undergo a single surgery for the extraction of the lower right and lower left third molars. Throughout the perioperative period, patients will be closely monitored, with their vital signs observed by both the surgical team and anesthesiology teams. As prophylaxis, patients will receive 900mg of clindamycin intravenously at the start of the procedure. The patient will be positioned supine on a hospital stretcher and placed under general anesthesia. Extra and intraoral antisepsis will be performed using a 0.12% chlorhexidine digluconate aqueous solution, and sterile surgical drapes will be used. Following these initial steps, one of the surgical sites (as selected) will be infiltrated with either 6 mL of 0.5% racemic bupivacaine + 0.2 mL of epinephrine or 4 mL of 0.75% ropivacaine with 0.2 mL of epinephrine, with approximately 25 mg of anesthetic injected. The surgical procedure will then begin. A Neumann incision with diverticulum will be made on the distal side of the adjacent mandibular second molar, followed by mucoperiosteal detachment, osteotomy, and odontosection (if necessary). The tooth will then be luxated and extracted using levers. The surgical wound will be cleaned and sutured with single or X-shaped stitches using 4-0 polyglactin sutures. Suture removal will take place between 7 and 10 days postoperatively. Before discharge, while

still in the hospital, patients will receive intravenous administration of 2g of dipyrone every 6 hours, 40mg of tenoxicam once daily, 100mg of tramadol every 8 hours, 600mg of clindamycin every 6 hours, and 4mg of ondansetron every 8 hours.

Postoperative instructions and necessary medications will be provided to patients both verbally and in writing, according to the protocol recommended by the hospital (APPENDIX B). Suture removal will be performed in an outpatient setting at the Hospital de Clínicas de Porto Alegre between 7 and 10 days postoperatively.

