4.9 EVALUATION OF POSTOPERATIVE ANALGESIA

To assess postoperative analgesia, a VAS will be used, in which patients will rate their pain from zero (no pain) to ten (worst pain ever felt) at different postoperative time points: T0 (immediate postoperative period, as soon as the patient is lucid), T1 (1 hour after T0), T2 (12 hours after T0), T3 (18 hours after T0), and T4 (24 hours after T0). Two scales will be used for each postoperative time point: one for the left side and one for the right side. These values will be recorded, compared, and presented in the results.

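### Appendix B bans rinsing for 48 hours but prescribes a 12-hourly chlorhexidine rinse from 24 hours after surgery, so both lines cannot be followed literally on day 2

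*Protocol*

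**What the plan says.** Protocol Appendix B is the care sheet for patients after the extractions. Among its general instructions is "Do not rinse your mouth for 48 hours". The next item is "Avoid spitting", with no time limit. Further down, under the medication heading, the same sheet says "Rinse with 10mL of 0.12% chlorhexidine digluconate aqueous solution for 1 minute every 12 hours for seven days, starting 24 hours after surgery".

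The sheet is operative text. Section 4.5 has it handed to patients after the operation. Section 4.6 says: "Postoperative instructions and necessary medications will be provided to patients both verbally and in writing, according to the protocol recommended by the hospital (APPENDIX B"). Section 4.4 adds that volunteers receive the unit's routine care without change. The sheet therefore appears to be the hospital's own, adopted by the protocol.

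The study outcomes are set elsewhere. Section 3.2 lists bleeding, vital signs and pain on a VAS. Sections 4.7 and 4.8 place vital signs and bleeding within the operation. Section 4.9 sets five pain ratings per side, the last 24 hours after T0, where T0 is the moment the patient is lucid after surgery.

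**The concern.** The two rinse lines sit on one page and address the same patient, and for part of the second day they ask for opposite things. A patient who keeps to the ban misses prescribed doses; a patient who takes the doses breaks the ban. Nothing on the page says which line gives way. The protocol relies on this sheet, together with a verbal explanation whose content is not recorded, so different patients may be left to settle the point in different ways.

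What is at stake is a clear and uniform care instruction over two fresh surgical sites. A statistician would also ask whether the ambiguity could reach any measured outcome.

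**Working it through.** The protocol derives no figure on this point, so there is nothing of its own to reproduce. The check compares two time windows and then sets them against the outcome schedule.

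**Inputs**

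- Ban: lasts 48 h, no exception, starting point not stated (Appendix B).
- Prescribed rinse: starts 24 h after surgery, every 12 h, for 7 days (Appendix B).
- Patients planned: 15 (Section 4.1, sample calculation).
- Last pain rating: T4 = T0 + 24 h (Section 4.9).

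**Rinse schedule.** Two rinses a day for 7 days gives 2 × 7 = 14 rinses. Rinse k is due at 24 + 12(k − 1) hours after surgery: 24, 36, 48, 60 h and so on.

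**Overlap if the ban runs from surgery (assumption).** The ban covers 0 to 48 h, so the overlap is 48 − 24 = 24 h.

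| Rinse | Due (h after surgery) | Position relative to the ban |
|---|---|---|
| 1 | 24 | inside |
| 2 | 36 | inside |
| 3 | 48 | on the boundary |
| 4 to 14 | 60 onwards | outside |

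That is 2/14 = 14% of scheduled rinses, or 3/14 = 21% with the boundary. Over 15 patients it is 15 × 2 = 30 rinses, or 15 × 3 = 45, out of 15 × 14 = 210.

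**Sensitivity to the unstated start.** Suppose the ban begins D hours after surgery, with D between 0 and 24. It then ends at 48 + D, and the overlap is (48 + D) − 24 = 24 + D hours. D = 0 gives 24 h; D = 12 gives 36 h. Starting the clock at surgery is therefore the assumption most favourable to the sheet. To remove the conflict, the ban would have to end by 24 h, meaning it began 24 h before the operation.

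**Could other wording resolve it?** The rinse line ends with a short pointer to the medications. It is attached to the prescription, not to the ban, and creates no exception. The ban is not limited to water, to vigorous rinsing or to unprescribed products. No section in the body of the protocol gives another rinse rule.

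**Reach into the outcomes.** Bleeding and vital signs are complete before the patient leaves the operating room. For pain, let L be the hours from surgery to T0 (not stated, and greater than zero). T4 then falls 24 + L hours after surgery, so the rinse due at 24 h can come L hours before T4. The rinse at 36 h could precede T4 only if L exceeded 12 h, and the one at 24 h could precede T3 (18 + L) only if L exceeded 6 h. Since T0 belongs to the immediate postoperative period, at most T4 is realistically in question. A mouth rinse reaches both extraction sites, so whatever it does to pain is largely shared by the two sides being compared.

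**The case against.** The best defence is that a specific, timed prescription can be read as an exception to a general behavioural rule, so that the ban covers only rinsing of the patient's own choosing. That reading is possible, but the sheet does not state it, and a lay reader should not have to infer it.

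A second defence is that this is a routine hospital hand-out and not a trial design decision, and that verbal instructions give patients a chance to ask. The first half is fair: this is an inconsistency in a care document, not a statistical fault. But the protocol adopts the sheet, and it does not record what the verbal explanation says.

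A third is that no trial result depends on it. That largely stands, as shown under the working.

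Three stronger readings are tempting, and the documents support none of them:

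- A reader might infer a safety problem. The protocol gives no information on what follows from rinsing, or from not rinsing, between 24 and 48 hours.
- A reader might infer that complication results would be distorted. Section 4.4 mentions complications only as part of clinical follow-up visits. They are not an objective in Section 3 and are not analysed in Section 4.10.
- A reader might infer that the pain comparison is biased. At most one disputed rinse is likely to precede T4, and it reaches both sides.

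**Conclusion.** The contradiction is real on the face of Appendix B. With the ban counted from surgery, two scheduled rinses per patient fall inside it and a third falls on its edge, over a 24-hour overlap that any later start would lengthen. Patients cannot literally follow both lines and may act differently; the documents do not show that they will, or that harm would result.

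The consequence for the trial is minor. The intraoperative outcomes are untouched, and the split-mouth VAS comparison should be little affected. The case for correction rests on giving every participant a sheet that can be followed, not on any threat to the results. The conclusion depends on one assumption, the start of the 48 hours, and only the length of the overlap changes with it.

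**What to change.** The clinical team should reconcile the two lines of Appendix B so that the sheet gives one consistent instruction for 24 to 48 hours, and should state the moment from which the 48 hours are counted. If the ban was never meant to cover the prescribed rinse, the sheet should say so. Which timing applies is a clinical decision, and none is proposed here. When the lines are revised, the team should also check that the spitting instruction is consistent with the outcome.

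The cost is a line or two of text, carried into the sheet actually handed out and into the verbal explanation. Sample size, data collection and analysis do not change.

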4.4 SAMPLE

The sample selection will consist of patients referred to the Oral and Maxillofacial Surgery Unit at the Hospital de Clínicas de Porto Alegre. The selected patients require bilateral extraction of lower third molars under general anesthesia, either due to the complexity of the surgery or due to systemic conditions that contraindicate local anesthesia. Patients who meet these criteria will follow the routine care protocol adopted by the team. During outpatient consultations, laboratory tests (including blood count, PT, aPTT, glucose, AST, ALT, and creatinine), imaging (CT scan of the skull and facial bones), and pre-anesthetic evaluation will be requested. If the tests are normal and cleared by the Anesthesiology team, patients will be placed on the waiting list and contacted when surgery is available. There will be no change to the routine care for patients volunteering in the study. The surgical procedures will be performed by the research team responsible for this study. The inclusion criteria will include patients aged 18 to 60, classified as ASA I or ASA II, who have impacted or semi-impacted lower third molars with similar positioning on both sides, according to the Pell and Gregory classification.³⁸

Patients who can undergo surgery under local anesthesia or who require additional procedures in the same surgical session, will be excluded from the sample. All patients, whether participating in the study or not, will have the right to withdraw from the study at any time without penalty.

Postoperative consultations will be conducted for follow-up, suture removal, and the evaluation and treatment of any potential postoperative complications.

Regarding general anesthesia, since this is a split-mouth study, both patients undergoing total intravenous anesthesia and general inhalational anesthesia will be included. Patients requiring additional intraoperative medications, which may interfere with the data, will be excluded. An example of this is patients receiving tranexamic acid during the procedure, as it could distort bleeding measurements between surgical sites.

The selection of the control group and experimental groups will be determined by a simple randomization in the immediate preoperative period. One surgical site will receive 0.5% bupivacaine + 0.2mL of epinephrine (GA) while the other site will receive 0.75% ropivacaine + 0.2mL epinephrine (GB).

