4.5 PREOPERATIVE CONDUCTS

Each patient selected for the study will be required to complete an Informed Consent Form (APPENDIX A) prior to the clinical procedures. If any participant disagrees with the terms outlined in the form, they will not be included in the study.

The patient's medical history will be taken during an outpatient appointment automatically scheduled via the GERCON system. During this appointment, the team will investigate the patient's current medical condition, other comorbidities, medication use, and known allergies. In addition to the physical examination, imaging tests (panoramic X-rays and/or CT scans) and laboratory tests will be requested. This consultation will also collect sociodemographic data from the sample, assess their health status, and identify any factors that may contraindicate their participation in the study. After the imaging and laboratory tests are completed at the Hospital de Clínicas de Porto Alegre, patients will be placed on the waiting list for surgery. Following the surgical procedure, patients will receive a postoperative care and instructions form (APPENDIX B), standardized medications, and medical notes, if necessary. The VAS (APPENDIX C) and instructions on how to use it will also be provided after the surgery.

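### Appendix B does not say whether 1 g of paracetamol is the tablet or the dose, so the written instruction can mean 4 g or 8 g a day

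*Protocol*

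**What the plan says.** The medication list in Appendix B has three tablet lines, all in the order drug, amount, number of tablets, interval, duration:

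- The line at issue reads "Paracetamol 1g, 2 tablets every 6 hours for three days".
- The antibiotic line, in the same layout, reads "Clindamycin 300mg, 2 tablets every 6 hours for seven days".
- The other analgesic line, with a single tablet per dose, reads "Ketorolac tromethamine 10mg, 1 tablet every 6 hours for three days".

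Paracetamol is mentioned nowhere else in the protocol. The in-hospital drugs in section 4.6 do not include it, and no section gives a paracetamol tablet strength, mg per dose, daily total or maximum.

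The sheet is an operative document. Section 4.5 says that after surgery "patients will receive a postoperative care and instructions form (APPENDIX B), standardized medications". Section 4.6 says that instructions and medications are "provided to patients both verbally and in writing, according to the protocol recommended by the hospital", and names Appendix B as that protocol. Section 6 says how postoperative medication is paid for, but gives no strengths.

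**The concern.** A dosing line that gives one amount and a number of tablets is complete only if the reader knows what the amount refers to. Here it could be each tablet or the pair, and the two readings differ by a factor of two. The only strength-like figure in the line is 1 g, so someone prescribing or dispensing from it could reasonably supply 1 g tablets. The patient would then follow the sheet exactly and take twice the dose of the other reading, and nothing in the protocol would prevent it.

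What is at stake is participant safety and uniform postoperative analgesia. The comparison of bupivacaine with ropivacaine is not at stake: each patient is their own control, and oral paracetamol acts on both sides.

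**Working it through.** The protocol states no daily paracetamol total, so there is no figure to reproduce. The check works out what the line implies on each reading, then asks whether the rest of the document settles which is meant.

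**Inputs.** From Appendix B: paracetamol 1 g, 2 tablets, every 6 hours, 3 days; clindamycin 300 mg, 2 tablets, every 6 hours; ketorolac 10 mg, 1 tablet, every 6 hours. From section 4.6: in-hospital intravenous clindamycin, "600mg of clindamycin every 6 hours". The 500 mg tablet is not in the document; it is the strength needed for two tablets to make 1 g (1 g ÷ 2).

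**Tablets taken, the same on both readings.** 24 h ÷ 6 h = 4 doses a day; 2 × 4 = 8 tablets a day; 8 × 3 = 24 tablets per course.

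**Paracetamol dose = tablet strength × tablets.**

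| | 1 g is the tablet | 1 g is the two-tablet dose |
|---|---|---|
| Tablet strength | 1 g | 500 mg |
| Per dose | 2 × 1 g = 2 g | 2 × 0.5 g = 1 g |
| Per day | 2 g × 4 = 8 g | 1 g × 4 = 4 g |
| Three days | 8 g × 3 = 24 g | 4 g × 3 = 12 g |

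A 1 g dose made from 1 g tablets would be one tablet every 6 hours, or 1 × 4 × 3 = 12 tablets per course. The printed two tablets therefore fit a 1 g dose only with a 500 mg tablet.

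**Which reading do the other lines support?**

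- Clindamycin, amount per tablet: 300 mg × 2 = 600 mg per dose, × 4 = 2,400 mg/day.
- Clindamycin, amount per dose: 300 mg × 4 = 1,200 mg/day.
- Clindamycin in hospital (section 4.6): 600 mg × 4 = 2,400 mg/day.
- Ketorolac: 10 mg × 1 × 4 = 40 mg/day on either reading, so it does not discriminate.

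The clindamycin line agrees with the in-hospital dose only when its amount is read per tablet. Applied to paracetamol, that convention gives 8 g/day. This is support, not proof: it rests on one parallel line, and the in-hospital dose is intravenous, which an oral dose need not match.

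**The case against.** The strongest reply is that the harm depends on a fact the protocol does not show. The patient takes two tablets every 6 hours whichever reading is right, so the dose is set by the strength prescribed and dispensed. Patients receive standardized medications and verbal instructions with the sheet, and if the hospital stocks only 500 mg tablets the dose is 4 g/day. The phrase can also be read naturally as a 1 g dose taken as two tablets. The protocol gives no paracetamol ceiling, so from the document alone the gap is a doubling and not a demonstrated overdose. The sheet is the hospital's own, and section 4.4 says "There will be no change to the routine care for patients volunteering in the study". The English text has other language slips, so this may be one more, and the wording patients actually saw is unknown. Paracetamol is neither a study drug nor an endpoint.

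Most of this stands as a limit on the claim. It does not show that anyone received or was meant to receive 8 g/day, and the point does not touch the design or the analysis. It does not remove the defect. The protocol adopts the sheet as its own appendix and directs that it be given to every participant. The safeguard relied on, a standard supply of known strength, is not written down in any section. A translation slip that leaves a twofold dose range in a patient instruction still needs correcting.

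**Conclusion.** The concern holds. The paracetamol line is defective because it does not identify what 1 g refers to, and no other part of the protocol resolves it. The gap between the readings is twofold: 2 g against 1 g per dose, 8 g against 4 g per day, 24 g against 12 g over three days. The list's own format favours the higher reading, and the lower one requires a tablet strength that is never named.

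Confidence is high that the strength is unclear. It does not extend to 8 g/day having been intended or supplied. The 4 g/day figure assumes 500 mg tablets and the 8 g/day figure assumes 1 g tablets; the document confirms neither. No outside dose limit has been used. This should be fixed as a safety and standardisation matter, with no consequence for the within-patient comparison.

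**What to change.** 1. Check the line against the hospital's source-language sheet.
2. Have the responsible clinicians confirm the intended dose.
3. Rewrite the line to give tablet strength, tablets per dose, mg per dose and total per day. If 4 g/day is what is meant, it could read: paracetamol 500 mg tablets, 2 tablets (1 g) every 6 hours, 4 g per day in total, for three days.
4. Make sure the strength prescribed and dispensed matches the sheet.

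The protocol does not make clear whether surgeries are finished: the Summary describes them in the past tense, section 5 in the future. If they are continuing, reissue the sheet before the next discharge and inform any patient still on the three-day course. If they are complete, correct the document and record which strength was supplied.

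The cost is one corrected line, a check of the source sheet and the supply, and a reissued sheet if needed. Design, sample size and analysis are unchanged.
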